9. STATISTICAL METHODOLOGY

9.1 General

Data listings will be provided for all data that is databased. Summary statistics and statistical analysis will only be presented for data where detailed in this SAP. For continuous data, summary statistics will include the arithmetic mean, arithmetic standard deviation (SD), median, min, max, and N; for log-normal data (e.g., the PK parameters: AUCs and C_{max}) the geometric mean and geometric CV% will also be presented. For categorical data, frequency count and percentages will be presented. Data listings will be provided for all subjects up to the point of withdrawal, with any subjects excluded from the relevant population highlighted. Summary statistics and statistical analyses will generally only be performed for subjects included in the relevant analysis population. For the calculation of summary statistics and statistical analysis, unrounded data will be used.

Mean change from baseline is the mean of all individual subject's change-from-baseline values. Each individual change from baseline will be calculated by subtracting the individual subject's baseline value from the value at the timepoint. The individual subject's change-from-baseline values will be used to calculate the mean change from baseline using a SAS procedure such as Proc Univariate.

Data analysis will be performed using SAS[®] Version 9.4 or greater.

9.2 Demographics and Subject Disposition

Subject disposition will be listed. The demographic variables age, sex, race, ethnicity, site ID, body weight, height, BMI, and eGFR will be summarized by group and listed. All other demographic variables will be listed only.

9.3 Pharmacokinetic Assessment

9.3.1 Pharmacokinetic Analysis

The PK parameter estimates will be determined using noncompartmental methods in the validated software program, Phoenix WinNonlin (Certara, Version 6.4 or later).

Plasma concentrations of LY3298176 will be used to determine the following PK parameters, when possible:

Parameter	Units	Definition
AUC(0-∞)	ng.h/mL	area under the concentration versus time curve from time zero to infinity
AUC(0-t _{last})	ng.h/mL	area under the concentration versus time curve from time zero to time t, where t is the last time point with a measurable concentration
%AUC(t _{last} -∞)	%	percentage of AUC that is due to extrapolation from the last measurable concentration to infinity
C _{max}	ng/mL	maximum observed drug concentration
t _{max}	h	time of maximum observed drug concentration
t _{1/2}	h	half-life associated with the terminal rate constant (λ_z) in noncompartmental analysis
CL/F	L/h	apparent total body clearance of drug calculated after extravascular administration
V _z /F	L	apparent volume of distribution during the terminal phase after extravascular administration
V _{ss} /F	L	apparent volume of distribution at steady state after extravascular administration

Additional PK parameters may be determined where appropriate. The software and version used for the final analysis will be specified in the CSR. Any exceptions or special handling of data will be clearly documented within the final study report.

PK analysis will, where possible, be carried out using actual postdose times recorded in the raw data. If actual times are missing, nominal times may be used with sponsor approval.

Formatting of tables, figures and abbreviations will follow the Eli Lilly Global PK/PD/TS Tool: NONCOMPARTMENTAL PHARMACOKINETIC STYLE GUIDE. The version of the tool effective at the time of PK analysis will be followed.

General PK Parameter Rules

- Actual sampling times will be used in the final analyses of individual PK parameters, except for non-bolus predose sampling times which will be set to zero.
- C_{max} and t_{max} will be reported from observed values. If C_{max} occurs at more than 1 time point, t_{max} will be assigned to the first occurrence of C_{max}.
- AUC parameters will be calculated using a combination of the linear and logarithmic trapezoidal methods (linear-log trapezoidal rule). The linear trapezoidal method will be applied up to t_{max} and then the logarithmic trapezoidal method will be used after t_{max}. The minimum requirement for the calculation of AUC will be the inclusion of at least 3 consecutive plasma concentrations above the lower limit of quantification (LLOQ), with at least one of these concentrations following C_{max}. AUC(0-∞) values where the

percentage of the total area extrapolated is more than 20% will be flagged. Any AUC(0-∞) value excluded from summary statistics will be noted in the footnote of the summary table. If AUC(0-∞) cannot be determined for all subjects an alternative AUC measure, such as AUC to a fixed time point, may be used in the assessment exposure between dose groups.

- Half-life ($t_{1/2}$) will be calculated, when appropriate, based on the apparent terminal log-linear portion of the concentration-time curve. The start of the terminal elimination phase for each subject will be defined by visual inspection and generally will be the first point at which there is no systematic deviation from the log-linear decline in plasma concentrations. $t_{1/2}$ will only be calculated when a reliable estimate for this parameter can be obtained comprising of at least 3 data points. If $t_{1/2}$ is estimated over a time window of less than 2 half-lives, the values will be flagged in the data listings. Any $t_{1/2}$ value excluded from summary statistics will be documented in the footnote of the summary table.
- A uniform weighting scheme will be used in the regression analysis of the terminal log-linear portion of the concentration-time curve.
- The parameters based on the predicted last quantifiable drug concentration (C_{last}) will be reported.

Individual PK Parameter Rules

- Only quantifiable concentrations will be used to calculate PK parameters with the exception of special handling of certain concentrations reported below the lower limit of quantification (BQL). Plasma concentrations reported as BQL will be set to a value of zero when all of the following conditions are met:
 - The compound is nonendogenous.
 - The samples are from the initial dose period for a subject or from a subsequent dose period following a suitable wash-out period.
 - The time points occur before the first quantifiable concentration.
- All other BQL concentrations that do not meet the above criteria will be set to missing.
- Also, where 2 or more consecutive concentrations are BQL towards the end of a profile, the profile will be deemed to have terminated and, therefore, any further quantifiable concentrations will be set to missing for the calculation of the PK parameters unless considered to be a true characteristic of the profile of the drug.

Individual Concentration vs. Time Profiles

- Individual concentrations will be plotted utilizing actual sampling times.
- The terminal point selections will be indicated on a semilogarithmic plot.

Average Concentration vs. Time Profiles

- The average concentration profiles will be graphed using scheduled (nominal) sampling times.
- The average concentration profiles will be graphed using arithmetic average concentrations.
- The predose average concentration for single-dose data from nonendogenous compounds will be set to zero. Otherwise, only quantifiable concentrations will be used to calculate average concentrations.
- Concentrations at a sampling time exceeding the sampling time window specified in the protocol, or $\pm 10\%$, will be excluded from the average concentration profiles.
- Concentrations excluded from the mean calculation will be documented in the final study report.
- A concentration average will be plotted for a given sampling time only if 2/3 of the individual data at the time point have quantifiable measurements that are within the sampling time window specified in the protocol or $\pm 10\%$. An average concentration estimated with less than 2/3 but more than 3 data points may be displayed on the mean concentration plot if determined to be appropriate and will be documented within the final study report.

Treatment of Outliers during Pharmacokinetic Analysis

Application of this procedure to all PK analyses is not a requirement. Rather, this procedure provides justification for exclusion of data when scientifically appropriate. This procedure describes the methodology for identifying an individual value as an outlier for potential exclusion, but does not require that the value be excluded from analysis. The following methodology will not be used to exclude complete profiles from analysis.

Data within an Individual Profile

A value within an individual profile may be excluded from analysis if any of the following criteria are met:

- For PK profiles during multiple dosing, the concentration of the predose sample exceeds all measured concentrations for that individual in the subsequent postdose samples.
- For PK profiles during single dosing of nonendogenous compounds, the concentration in a predose sample is quantifiable.
- For any questionable datum that does not satisfy the above criteria, the profile will be evaluated and results reported with and without the suspected datum.

Data between Individual Profiles

1. If $n < 6$, then the dataset is too small to conduct a reliable range test. Data will be analyzed with and without the atypical value, and both sets of results will be reported.
2. If $n \geq 6$, then an objective outlier test will be used to compare the atypical value to other values included in that calculation:
 - a. Transform all values in the calculation to the logarithmic domain.
 - b. Find the most extreme value from the arithmetic mean of the log-transformed values and exclude that value from the dataset.
 - c. Calculate the lower and upper bounds of the range defined by the arithmetic mean $\pm 3*SD$ of the remaining log-transformed values.
 - d. If the extreme value is within the range of arithmetic mean $\pm 3*SD$, then it is not an outlier and will be retained in the dataset.
 - e. If the extreme value is outside the range of arithmetic mean $\pm 3*SD$, then it is an outlier and will be excluded from analysis.

If the remaining dataset contains another atypical datum suspected to be an outlier and $n \geq 6$ following the exclusion, then repeat step 2 above. This evaluation may be repeated as many times as necessary, excluding only 1 suspected outlier in each iteration, until all data remaining in the dataset fall within the range of arithmetic mean $\pm 3*SD$ of the log-transformed values.

Reporting of Excluded Values

Individual values excluded as outliers will be documented in the final report. Approval of the final report will connote approval of the exclusion.

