Abbreviations: $AUC_{0-\infty}$ = area under the concentration versus time curve from time zero to infinity; $AUC_{0-t_{last}}$ = area under the concentration versus time curve from time zero to the time of last measured concentration; C_{max} = maximum drug concentration; ESRD = end-stage renal disease; PK = pharmacokinetic; SC = subcutaneous.

Summary of Study Design:

Study I8F-MC-GPGG is a Phase 1, multicenter, nonrandomized, open-label, parallel-design study in subjects with mild, moderate, or severe renal impairment, or end-stage renal disease (ESRD), and control subjects with normal renal function. Renal function will provide the basis for assignment to treatment group.

- Group 1: control subjects with normal renal function (estimated glomerular filtration rate [eGFR] ≥ 90 mL/min/1.73m²)
- Group 2: subjects with mild renal impairment (eGFR between 60 and 89 mL/min/1.73m²)
- Group 3: subjects with moderate renal impairment (eGFR between 30 and 59 mL/min/1.73m²)
- Group 4: subjects with severe renal impairment (eGFR <30 mL/min/1.73m² and not requiring dialysis)
- Group 5: subjects with ESRD (have received dialysis for at least 3 months).

Subjects with T2DM and renal impairment will be permitted to enroll in the study. Subjects with T2DM will not be included in Group 1.

Treatment Arms and Planned Duration for an Individual Subject:

Subjects will be screened over a 28-day period prior to dosing. Subjects will be admitted to the clinical research unit (CRU) on Day -1, receive a single subcutaneous injection of LY3298176 on Day 1, remain at the CRU until discharge on Day 5, and return to the CRU on Days 8 and 15 for PK blood sampling and other study procedures. Subjects will also return to the CRU for a follow-up visit at least 28 days postdose for final PK and study assessments.

Subjects will receive either 5 mg LY3298176 or, depending on interim analysis results, a dose of LY3298176 reduced by approximately 50%.

Number of Subjects:

Approximately 58 subjects will be enrolled so that approximately 48 subjects complete the study, such that approximately 8 subjects per group complete Groups 2 through 5. Approximately 16 completers are needed from Group 1 in order to facilitate demographic matching with the subjects in other groups.

Statistical Analysis:

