Following administration of a single dose of LY3298176, the maximum drug concentration (C_{max}) was observed to occur between 8 and 96 hours. The mean terminal half-life was approximately 5 days, thus supporting a QW dosing regimen. Pharmacokinetic data from the Phase 1 study supports apparent dose-proportionality of LY3298176.

Based on preliminary data, 52 subjects (out of 142 subjects dosed in this study) received 4.5 mg (6 healthy subjects) to 5 mg as a single dose or as the first dose (32 T2DM out of 47 subjects). There were no reported LY3298176-related SAEs.

Overall, gastrointestinal events (eg, vomiting, abdominal distension, nausea, diarrhea) were the most frequently reported adverse events (AEs). These AEs increased in number and severity with increasing doses, and higher doses appeared to be better tolerated when LY3298176 was administered via dose titration. The reported gastrointestinal- (GI-) related AEs are consistent with GLP-1 pharmacology and those observed previously following administration of GLP-1 receptor agonists (RAs) (Nauck et al. 2009; Dungan et al. 2014; Giorgino et al. 2015; Jendle et al. 2016; Nauck et al. 2016).

In Part A (SAD) of Study GPGA, with increasing doses there was an increase in the number and severity of AEs related to LY3298176. At the 5-mg dose, 6 subjects reported a total of 23 AEs that were all mild in severity. At the 8-mg dose, 7 subjects reported a total of 31 AEs, 21 of which were mild and 10 moderate in severity. Two of 6 subjects who received the 5-mg dose reported 5 mild AEs of vomiting and 1 subject reported a mild AE of nausea, whereas at the 8-mg dose, 3 of 7 subjects reported 12 episodes of vomiting, and 4 of 7 subjects reported 4 AEs of nausea. Two subjects who received 8 mg as a single dose and reported AEs of vomiting and nausea required treatment with antiemetics and IV fluids. Further dose escalation was stopped and the 5-mg dose was considered the maximum tolerated dose.

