10.3.2. Pharmacokinetic Analyses

10.3.2.1. Pharmacokinetic Parameter Estimation

Pharmacokinetic parameter estimates for LY3298176 will be calculated by standard noncompartmental methods of analysis.

The primary parameters for analysis will be area under the concentration versus time curve (AUC) from time zero to infinity ($AUC_{0-\infty}$), AUC from time zero to the time of last measured concentration ($AUC_{0-tlast}$), and maximum drug concentration (C_{max}). Other noncompartmental parameters, such as half-life, apparent clearance, and apparent volume of distribution, may be reported.

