11. CHANGES FROM THE PROTOCOL SPECIFIED STATISTICAL ANALYSES

There were no changes from the protocol specified statistical analyses.

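### SAP 9.3.1 lists Vss/F, but noncompartmental analysis of a single SC dose overstates it because the residence time includes absorption

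*SAP*

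**What the plan says.** SAP 9.3.1 states that "The PK parameter estimates will be determined using noncompartmental methods". It then says that plasma concentrations "will be used to determine the following PK parameters, when possible", followed by a table. Two of its entries are volumes: Vz/F for the terminal phase, and Vss/F, the "apparent volume of distribution at steady state after extravascular administration". Both also appear in the SAP abbreviations (section 2). The SAP gives no formula for Vss/F, lists neither MRT nor mean absorption time, and describes no correction for absorption.

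On the design, the protocol synopsis says that subjects "receive a single subcutaneous injection of LY3298176 on Day 1". No intravenous arm exists.

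Protocol 10.3.2.1 names AUC(0-∞), AUC(0-tlast) and Cmax as primary and adds that other parameters such as "half-life, apparent clearance, and apparent volume of distribution, may be reported". The ANOVA in SAP 9.3.2 covers only the three primary parameters; tmax has a separate Wilcoxon test.

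**The concern.** Noncompartmental Vss is clearance multiplied by the mean residence time of drug once it is in the body (the disposition MRT). After a subcutaneous dose, AUMC/AUC measures that time plus the time spent being absorbed. Subcutaneous data alone cannot separate the two without assuming a model. The product CL/F × AUMC/AUC is therefore a mixture of distribution and absorption, yet it would be tabulated under a name that means distribution only.

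SAP 9.1 calls for summary statistics on continuous data detailed in the SAP, and section 6 orders the outputs by renal group, so a Vss/F summary by group is the natural product. If one group absorbed the drug more slowly, its Vss/F would be higher with no change in distribution, and a reader of a renal impairment report could take that as a real change in volume.

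**Working it through.** The plan states no figure for Vss/F, so there is none to reproduce. The check is the moment identity, followed by an illustration of size.

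**Identity (no compartmental model needed).** With MAT the mean absorption time:

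- AUMC/AUC after an SC dose = disposition MRT + MAT
- Vss/F = CL/F × disposition MRT
- Computed value = CL/F × AUMC/AUC = Vss/F + CL/F × MAT

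The excess is CL/F × MAT. It is never negative.

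**Inputs for size.** Protocol 3.2 reports that after a single dose Cmax "was observed to occur between 8 and 96 hours" and that "The mean terminal half-life was approximately 5 days", taken here as 120 h.

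**Assumption.** One compartment with first-order absorption. Then:

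- ke = ln 2 / 120 = 0.005776 per h, so disposition MRT = 1/ke = 173.1 h
- ka is solved from tmax = ln(ka/ke) / (ka − ke)
- MAT = 1/ka
- computed/true Vss/F = (1/ke + 1/ka) / (1/ke) = 1 + ke/ka

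For tmax 24 h: ka = 0.138 per h, MAT = 7.25 h, AUMC/AUC = 173.1 + 7.25 = 180.4 h, ratio = 180.4/173.1 = 1.042.

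| tmax (h) | ka (per h) | MAT (h) | AUMC/AUC (h) | computed/true Vss/F |
|---|---|---|---|---|
| 8 | 0.5825 | 1.7 | 174.8 | 1.01 |
| 24 | 0.1380 | 7.3 | 180.4 | 1.04 |
| 48 | 0.0513 | 19.5 | 192.6 | 1.11 |
| 72 | 0.0274 | 36.5 | 209.6 | 1.21 |
| 96 | 0.0171 | 58.6 | 231.8 | 1.34 |

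**Contrast between two groups with identical CL/F and V/F.** The false ratio is the quotient of two table rows. For tmax 24 h versus 48 h it is 1.1127/1.0419 = 1.07. For the extremes, 8 h versus 96 h, it is 1.3387/1.0099 = 1.33.

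**Check on the planned sampling.** Noise-free profiles were analysed by the SAP rules: linear trapezoids to tmax and logarithmic after, with predicted Clast. The terminal slope was taken from the last three points. Times were 0, 8, 12, 24, 48, 72, 96, 168, 336 and 648 h; the last is nominal Day 28, whereas a visit at least 28 days postdose would fall at 672 h or later.

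| tmax contrast | Vss/F ratio | Vz/F ratio |
|---|---|---|
| 24 h vs 48 h | 1.07 | 1.00 |
| 24 h vs 72 h | 1.17 | 1.01 |
| 8 h vs 96 h | 1.32 | 1.06 |

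The Vss/F ratios agree closely with the formula. Vz/F, computed from the same profiles, is much less sensitive to absorption.

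**The case against.** The strongest reply is that very little rests on Vss/F. It is outside the ANOVA, the protocol makes volume terms optional, and the planned tmax comparison would help a reader recognise an absorption effect. This stands, and it keeps the point minor.

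A second reply is that the qualifier on the parameter list lets the analyst leave Vss/F out. It does permit that, but nothing directs it. Software will return a number for any profile with an estimable terminal slope, so the qualifier screens out sparse profiles rather than an unsuitable parameter. The SAP's silence on the formula also leaves room for a correction, but none is stated and the design supplies no intravenous data for one.

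A third reply concerns size. The 8 to 96 h range is the spread of observed tmax in an earlier study, not a difference between renal groups. Observed tmax can fall only on a sampled time, so its extremes may exaggerate the true spread in absorption. For tmax of 24 to 48 h the overstatement is 4% to 11%. The resulting ratio of 1.07 is 0.068 on the log scale, about a quarter of the 0.29 half-width planned for AUC and Cmax. If Vss/F varied about as much as those (an assumption), such a shift would be hard to see with 8 subjects per group. This also stands.

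Three stronger readings are tempting but unsupported:

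- A reader might infer that the renal groups will show a false volume difference. That needs absorption to differ by group, and nothing in the documents says renal impairment changes subcutaneous absorption. A shift in group tmax from 24 h to 72 h is hypothetical.
- A reader might infer that Vss/F bears on a mechanism proposed in protocol 5.4. That section says only that expected albumin binding makes a meaningful renal effect less likely; it does not discuss altered binding or fluid distribution.
- A reader might infer that SAP section 11 is wrong to say "There were no changes from the protocol specified statistical analyses". The protocol's list of other parameters is open and speaks of apparent volume generically, so naming Vss/F does not contradict it.

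**Conclusion.** The point holds as a minor one. By the planned method, CL/F × AUMC/AUC after a single SC dose is not Vss/F; it exceeds it by CL/F × MAT. That direction follows from the moment identity. The size, about 1% to 34% over the tmax range in protocol 3.2, depends on the assumed one-compartment, first-order model, the 120 h half-life, and use of the uncorrected MRT. Any false contrast between groups also requires absorption to differ between them. The primary AUC and Cmax comparisons do not use Vss/F and are unaffected.

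**What to change.** Delete Vss/F from the SAP 9.3.1 table and from the SAP abbreviations. Keep Vz/F, which needs only CL/F and the terminal slope and fits the protocol's wording on apparent volume. If a residence-time measure is wanted, report MRT(0-∞) labelled as including absorption.

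The cost is one line in each of the two places, plus the same removal from the TFL shells if Vss/F appears there; the shells are a separate document that could not be checked. No data collection changes and no valid information is lost.

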9.3.2 Pharmacokinetic Statistical Methodology

The main analysis is the evaluation of log-transformed $AUC(0-\infty)$, $AUC(0-t_{last})$, and C_{max} using an analysis of variance model with subject group as a fixed factor. The 90% confidence interval of the ratio between each impaired renal function group versus the control group will be estimated.

Example SAS code:

```
proc mixed data=DATA;
  class group;
  model log_pk = group / ddfm=kr;
  lsmeans group / pdiff cl alpha=0.1;
  ods output lsmeans=lsmeans;
  ods output diffs=diffs;
run;
```

The above analyses will be conducted twice, using different renal function group assignments (eGFR or creatinine clearance [CLcr] based on Day -1 measurements) (Table 2). The analysis based on CLcr will be exploratory.

Table 2. Renal Function Classification for Primary and Exploratory Analyses

Group	Classification	eGFR (mL/min/1.73m ²) ^a	CLcr (mL/min) ^b
1	Control (normal renal function)	≥90	≥90
2	Mild renal impairment	60-89	60-89
3	Moderate renal impairment	30-59	30-59
4	Severe renal impairment	15-29	15-29
5	End-stage renal disease	Requiring dialysis	Requiring dialysis

Abbreviations: CLcr = creatinine clearance; eGFR = estimated glomerular filtration rate.

^a Per enrollment classification; eGFR will be calculated using the Modification of Diet in Renal Disease abbreviated equation.

^b CLcr will be calculated using the Cockcroft-Gault formula (Cockcroft and Gault 1976).

The supporting additional analysis is the evaluation of the relationship between the PK of LY3298176 and mean eGFR, as determined by the MDRD abbreviated equation. Scatter plots of PK parameter versus eGFR will be produced and analyzed using either a mixed-effects linear or a nonlinear regression approach with eGFR as a continuous covariate on PK parameters.

t_{max} will be analyzed using a Wilcoxon rank sum test.

If a dose adjustment after interim is needed, descriptive statistics for the PK parameters will be summarized by dose and subject groups. Dose normalization or other methods may be employed for statistical analyses.

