3. INTRODUCTION

This SAP has been developed after review of the Clinical Study Protocol (final version dated 15 January 2018).

This SAP describes the planned analysis of the pharmacokinetic (PK) and tolerability data from this study. A detailed description of the planned TFLs to be presented in the clinical study report (CSR) is provided in the accompanying TFL shell document.

The intent of this document is to provide guidance for the statistical and PK analyses of data. In general, the analyses are based on information from the protocol, unless they have been modified by agreement between Eli Lilly and Company and Covance Early Clinical (EC) Biometrics. A limited amount of information concerning this study (e.g., objectives, study design) is given to help the reader's interpretation. This SAP must be signed off prior to first subject administration for this study. When the SAP and TFL shells are agreed upon and finalized, they will serve as the template for this study's CSR.

This SAP supersedes the statistical considerations identified in the protocol; where considerations are substantially different, they will be so identified. If additional analyses are required to supplement the planned analyses described in this SAP, they may be performed and will be identified in the CSR. Any substantial deviations from this SAP will be agreed upon between Eli Lilly and Company and Covance EC Biometrics and identified in the CSR. Any minor deviations from the TFLs may not be documented in the CSR.

This SAP is written with consideration of the recommendations outlined in the International Council on Harmonisation (ICH) E9 Guideline entitled Guidance for Industry: Statistical Principles for Clinical Trials¹ and the ICH E3 Guideline entitled Guidance for Industry: Structure and Content of Clinical Study Reports².

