5. STUDY DESIGN

This is a Phase 1, parallel-design, open-label, multicenter, single-dose study to assess PK and tolerability of a single dose of LY3298176 in subjects with mild, moderate, or severe renal impairment, or ESRD, and control subjects with normal renal function. Control Group 1 will be healthy subjects with normal renal function. Subjects with Type 2 Diabetes Mellitus (T2DM) will not be included in Group 1. Subjects with T2DM and renal impairment will be permitted to enroll in Groups 2 to 5, whereas subjects with T2DM and normal renal function will not be permitted. Subjects will be assigned to 1 of 5 groups (Groups 1 to 5) based on criteria outlined in [Table 1](#). Estimated glomerular filtration rate (eGFR) will be determined by the Modification of Diet in Renal Disease (MDRD) abbreviated equation using serum creatinine levels obtained at Screening and on Day -1; subjects will be assigned to groups based on values from Day -1.

The control subjects (Group 1) will be selected in order that the mean and distribution of Group 1 are comparable to the mean and distribution for each group with renal impairment (Groups 2 through 5) for age (± 10 years), sex, race, weight (± 10 kg), and body mass index (BMI) ($\pm 20\%$), as far as is practically possible³.

Table 1. Subject Groups based on Renal Impairment Status

	Classification	eGFR (mL/min/1.73m ²)
Group 1	Control (normal renal function)	≥ 90
Group 2	Mild renal impairment	60-89
Group 3	Moderate renal impairment	30-59
Group 4	Severe renal impairment	15-29
Group 5	End-stage renal disease	Requiring dialysis

[figure not shown]
Abbreviations: eGFR = estimated glomerular filtration rate (as determined by the Modification of Diet in Renal Disease abbreviated equation).

[Figure 1](#) and [Figure 2](#) illustrate the study design.

Subjects will visit the Clinical Research Unit (CRU) to sign the informed consent document and undergo screening procedures up to 28 days prior to dosing.

[figure not shown]
Subjects will be admitted to the CRU on Day -1. Subjects will be administered a single dose of LY3298176 on Day 1 and will remain in the CRU until after assessments are completed on Day 5. Subjects will return for study visits on Days 8 and 15 and for a final follow-up visit at least 28 days postdose.

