7. SAMPLE SIZE JUSTIFICATION

Approximately 58 subjects will be enrolled so that approximately 48 subjects complete the study, such that approximately 8 subjects per group complete Groups 2 through 5. Approximately 16 completers are needed from Group 1 in order to facilitate demographic matching with the subjects in other groups.

The sample size is not selected to satisfy an a priori statistical requirement. However, the sample size (16 subjects for the control group and 8 subjects per group for the other groups) will provide a 90% coverage probability of the half-width of the 90% confidence interval within 0.29 on a log-scale for comparison of each group to the control group for the area under the concentration versus time curve (AUC) or maximum observed drug concentration (C_{max}), assuming the variability (coefficient of variation [CV]) is 32%. In the natural scale, assuming the ratio is r , the 90% confidence interval for the ratio should be within (0.74 r , 1.34 r).

Subjects who are enrolled but not administered treatment may be replaced to ensure that a sufficient number of subjects complete the study.

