8. DEFINITION OF ANALYSIS POPULATIONS

The “Safety” population will consist of all enrolled subjects, whether or not they completed all protocol requirements.

The “Pharmacokinetic” population will consist of all subjects who received at least one dose of study drug and have evaluable PK data.

All protocol deviations that occur during the study will be considered for their severity/impact and will be taken into consideration when subjects are assigned to analysis populations.

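### SAP Tables 1 and 2 keep the superseded 15-29 range for Group 4, so non-dialysis subjects below 15 are handled inconsistently in the primary eGFR ANOVA and have no group in the exploratory CLcr ANOVA

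*SAP*

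**What the plan says.** **SAP.** Section 5, Table 1, has the row "Group 4 Severe renal impairment 15-29". Section 9.3.2, Table 2, which sets the groups for the ANOVA, has "Severe renal impairment 15-29 15-29": the first range is eGFR, the second CLcr. Group 5 in the same table requires dialysis. Footnote a, attached to the eGFR column only, reads "Per enrollment classification; eGFR will be calculated using the Modification of Diet in Renal Disease abbreviated equation". Footnote b, for CLcr, gives only the Cockcroft-Gault formula. The ANOVA is run once with each grouping, and "The analysis based on CLcr will be exploratory". The supporting regression is fitted "with eGFR as a continuous covariate on PK parameters". The PK population in Section 8 is "all subjects who received at least one dose of study drug and have evaluable PK data", with no lower limit on eGFR.

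**Current protocol.** The synopsis, Table GPGG.2 (Section 5.1) and both columns of Table GPGG.3 (Section 10.3.2.2) define Group 4 as below 30 and not requiring dialysis. Subjects are assigned to groups on Day -1 values (Sections 5.1 and 7.2).

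**Versions.** SAP Section 3 names the protocol dated 15 January 2018 as its basis. Amendment (b) was approved on 3 May 2019. Section 3 also says that the SAP takes precedence over the protocol's statistical considerations and that substantial differences will be identified. Section 11 reports none.

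**The concern.** Amendment (b) widened Group 4 because severe subjects were hard to recruit (Protocol Appendix 9). The newly eligible people are those below 15 and not on dialysis, and these are the people the SAP's range omits. They cannot go to Group 5, which needs dialysis.

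Two programmers working from SAP Table 2 could therefore build different severe groups for a primary ratio. One would apply the printed range and the other the footnote. The study is open-label and has interim PK reviews, so a rule left open could be settled after concentrations have been seen. The choice also decides whether the severe-versus-control ratio covers the lowest non-dialysis renal function, in a study meant to support dose recommendations across degrees of impairment (Protocol Section 3.1).

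The continuous eGFR regression uses no cut-offs and is unaffected. The problem is confined to the group contrasts.

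**Working it through.** **1. Where each document puts a non-dialysis subject below 15**

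| Analysis | Current protocol | SAP Table 2, printed range | SAP Table 2, footnote |
|---|---|---|---|
| Primary ANOVA (eGFR below 15) | Group 4 | no row | a: enrolled group, so Group 4 |
| Exploratory ANOVA (CLcr below 15) | Group 4 | no row | b: formula only, no group |

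For eGFR, the range and the footnote disagree. For CLcr, nothing in the SAP supplies a group. The CLcr gap can also catch a subject enrolled with eGFR 15-29. CLcr comes from a different formula and is in mL/min rather than mL/min/1.73 m², so the two values need not fall in the same band.

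**2. The plan's own precision figure**

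SAP Section 7 states a "90% coverage probability of the half-width of the 90% confidence interval within 0.29 on a log-scale", for 16 controls against 8 per impaired group at a CV of 32%.

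- σ = √ln(1 + 0.32²) = 0.3122
- Pooled df for the five-group ANOVA = 48 − 5 = 43. For two groups alone, 16 + 8 − 2 = 22.
- Half-width = t(0.95, df) × s × √(1/16 + 1/n₄), where n₄ is the number in Group 4
- P(half-width ≤ 0.29) = P(χ² with df ≤ df × [0.29 / (t(0.95, df) × σ × √(1/16 + 1/n₄))]²)

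At n₄ = 8 this gives 0.994 (df 43) or 0.955 (df 22). With 0.32 taken directly as the log-scale SD it gives 0.988 or 0.934. The stated 90% is not reproduced exactly, but it is met with a margin, so the plan's figure is conservative.

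**3. If the printed range were applied and k of the 8 removed**

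The documents give no count below 15, so k = 0 to 4 is an assumed range. The SE ratio is √(1/16 + 1/(8 − k)) / √(1/16 + 1/8). The pooled df is 43 − k and the two-group df is 22 − k.

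| k | n₄ | SE ratio | 90th percentile of half-width (pooled) | P(≤ 0.29), pooled df | P(≤ 0.29), two-group df |
|---|---|---|---|---|---|
| 0 | 8 | 1.000 | 0.258 | 0.994 | 0.955 |
| 1 | 7 | 1.047 | 0.270 | 0.978 | 0.904 |
| 2 | 6 | 1.106 | 0.286 | 0.923 | 0.810 |
| 3 | 5 | 1.183 | 0.307 | 0.773 | 0.657 |
| 4 | 4 | 1.291 | 0.335 | 0.481 | 0.444 |

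The SAP's model pools the variance over all five groups, so the pooled column applies. There the 90% target survives one or two removals and fails at three. On two-group df it fails at two.

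For the CLcr ANOVA these figures are illustrative only, because re-grouping also changes the other group sizes.

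**The case against.** The best defence is that footnote a already gives the primary rule. Enrolment follows the current protocol, the group is fixed on Day -1 before dosing, no text tells anyone to exclude a subject below 15, and the PK population has no floor. On that reading 15-29 is a stale number beside a footnote that overrides it, and the primary estimate does not change. SAP Table 1 is only background, since Section 3 describes the design information as an aid to the reader. The CLcr analysis is exploratory, and protocol Table GPGG.3 does give those subjects a group. Every non-zero figure above needs both subjects below 15 and a decision to exclude them.

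Much of this stands. Footnote a favours keeping these subjects, so the primary problem is an ambiguity and not an instruction to exclude. The range of sizes is conditional. The 15-29 range also looks like version lag and not a deliberate override, because Section 11 declares no change.

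Two points survive. First, Table 2 still prints a numerical range that conflicts with its own footnote for a primary contrast. Second, protocol Table GPGG.3 does not cure the CLcr column. It sits in the protocol's statistical section, over which the SAP claims precedence, and SAP Table 2 followed as written has no row for the subject.

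**Conclusion.** The concern holds. The SAP's operative Group 4 definition is out of date against the current protocol. The result is an ambiguity in the primary eGFR ANOVA and an undefined group in the exploratory CLcr ANOVA. Section 11's statement that nothing changed may have been right against the 2018 protocol, but it is not right against the current one.

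The size depends on an unknown count. The primary effect is zero if no enrolled non-dialysis subject is below 15, or if the enrolled group is carried forward. If one or two of eight were excluded, the standard error would rise by 5% or 11% and the stated precision would still be met on pooled df. At three or four it would rise by 18% or 29% and the precision target would be missed. These figures assume 16 controls, 8 planned completers in each other group, a CV of 32% and a common variance. The point should be settled before analysis because it touches a primary contrast.

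**What to change.** Update the SAP to Amendment (b) before analysis:

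- Replace 15-29 with the protocol's definition (below 30, not requiring dialysis) in Table 1 and in both columns of Table 2.
- State in Section 9.3.2 that the primary ANOVA uses the group assigned under the protocol on Day -1.
- Cite the current protocol version in Section 3 and revise Section 11 to match.

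This is a change of SAP wording only. It needs no new data or subjects and leaves the model unchanged.
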